3.2 Exploratory Objectives

The exploratory objectives for this study are:

- To evaluate the change in quality of life (QoL) from baseline.
- To evaluate duration of response.
- To evaluate OR by standard-risk and high-risk GvHD at onset ([MacMillan et al., 2015](#)).

4.0 INVESTIGATIONAL PLAN

4.1 Summary of Study Design

This will be a prospective, multicenter, randomized, open-label, phase II/III clinical study in which subjects will be randomly assigned in a 1:1 ratio to receive BEGEDINA treatment or the best conventional treatment. Randomization will be stratified by the baseline GvHD severity grade to either Grade B GvHD or Grade C/D GvHD.

The study will be conducted at approximately 30 bone marrow transplantation units in Europe, US and Canada. It is planned to enroll 184 subjects with steroid-resistant acute GvHD. The subjects will be randomized (1:1) to one of two treatment arms:

- BEGEDINA IV at a dose of 2.7 mg/m²/day for 5 consecutive days from Study Day 1 through to Study Day 5, and on Study Days 10, 14, 17, 21, 24, and 28.*
- Conventional second-line treatment: a single treatment (agent), chosen at the discretion of the investigator (physician's best choice) and based on the clinical conditions of the individual subject. The treatment will be given as per prescribing instructions (and/or standard practice of the center).

Patients in both arms are to continue (or initiate) baseline therapy of methylprednisolone (or other steroid equivalent) and calcineurin inhibitor (see Section 5.7.2.4.1).

*Please note: the term "Study Day" as used throughout the protocol is used in relation to the day that randomized study treatment started and not in relation to the day of transplant.

All subjects will undergo a screening visit to assess for eligibility and for screening assessments; this visit must take place within 2 days of Baseline. After screening, subjects will undergo randomization and the baseline visit, which is also the first day of study treatment (Study Day 1) (i.e., subjects must commence study treatment within two days of meeting eligibility). Study visits will be conducted at various timepoints (Table 19) through Study Day 180.

The experimental phase of the study will end for each subject on Study Day 180. An extended, long-term, observational follow-up is also planned in order to capture survival, response/relapse, glucose metabolism, health outcomes and safety data out to Study Day 180. Thus, the expected duration for an individual subject who completes the study according to the protocol will be approximately 6 months, including screening and 180-day follow-up.

Table 19 Schedule of Events

Study Day Visit Windows Assessments	Screening ^a	Experimental Phase																		Early Withdrawal	
		BEGEDINA Treatment Period																			
	-2 to -1	BL ^{a/1}	2	3	4	5	6	7	8	9	10	14	17	21	24	28	56	90	180 ^b		
											±1	±1	±1	±1	±1	±1	±2	±7	±7		
Informed Consent	X																				
Inclusion/exclusion criteria	X	X																			
Demographics	X																				
Complete medical/surgical history	X ^c																				
Transplant history	X ^d																				
Transplant medications	X ^e																				
Prior and concomitant medications ^f	X	X – To be assessed at each visit and recorded through Study Day 58 or up to 30 days after the last dose of study treatment, whichever is later ^f																			
Complete physical examination ^{g,h}	X	X				X					X	X		X		X	X	X	X		
Height and weight ^{g,i}	X	X				X					X	X		X		X	X	X	X		
Oxygen saturation ^{g,j}	X	X	X	X	X	X					X	X		X		X	X	X	X		

Study Day Visit Windows Assessments	Screening ^a	Experimental Phase																		Early Withdrawal
		BEGEDINA Treatment Period																		
	-2 to -1	BL ^{a/1}	2	3	4	5	6	7	8	9	10	14	17	21	24	28	56	90	180 ^b	
											±1	±1	±1	±1	±1	±1	±2	±7	±7	
Vital signs ^{g,j}	X	X				X					X	X		X		X	X	X		
12-lead ECG ^k	X	X				X						X				X				
Laboratory safety ^{g,l}	X	X	X	X	X	X					X	X		X		X	X	X	X ^s	
Pregnancy test ^m	X																			
Glucose metabolism ⁿ		X														X			X	X
Infection markers ^o	X															X ^o	X			
Karnofsky PS ^{g,p}	X	X				X					X	X		X		X	X	X	X	X
Acute GvHD assessment, organ staging ^q	X	X	X	X	X	X					X	X	X	X	X	X	X	X		
Adverse events ^w	X	X – All AEs to be assessed at each visit and recorded through Study Day 58 or up to 30 days after the last dose of study treatment, whichever is later ^w																		
QoL evaluation ^r	X															X		X	X ^s	
Randomization		X																		
Administration of BEGEDINA		X	X	X	X	X					X	X	X	X	X	X				

Study Day Visit Windows Assessments	Screening ^a	Experimental Phase																		Early Withdrawal
		BEGEDINA Treatment Period																		
	-2 to -1	BL ^a /1	2	3	4	5	6	7	8	9	10	14	17	21	24	28	56	90	180 ^b	
											±1	±1	±1	±1	±1	±1	±2	±7	±7	
Administration of conventional treatment		Per Prescribing information for selected conventional treatment																		
Overall survival		To be assessed/recorded at each visit through Day 180 (excluding Days 6 through 9)																		
TRM		To be assessed/recorded at each visit through Day 180 (excluding Days 6 through 9)																		
PK blood sample ^s		X				X					X	X	X	X	X	X				
HAMA blood sample ^t		X				X					X	X	X	X	X	X	X	X		
Steroid use (route, dose duration)		To be assessed/recorded at each visit through Day 90																		
Response to treatment																	X ^u	X	X	
Relapse		To be assessed/recorded at each visit through Day 180 (excluding Days 6 through 9)																		
Second malignancy		To be assessed/recorded at each visit through Day 180 (excluding Days 6 through 9)																		
Chronic GvHD assessment ^v		X	X	X	X	X					X	X	X	X	X	X	X	X	X	X

Abbreviations: BL, baseline; CT, computed tomography; ECG, electrocardiogram; GvHD, graft-versus-host disease; HAMA, human anti-mouse antibody; PK, pharmacokinetic(s); PS, performance status; QoL, quality of life; TRM, transplant-related mortality.

- ^a Screening, randomization and the first administration of study treatment may occur on the same day if the study treatment is maintained at the study center. If baseline occurs on the same day as screening, then there is no need to repeat any evaluations that have already been done as screening assessments. However, before administering the drug, vital signs should be measured and oxygen saturations collected.
- ^b Every effort should be made to arrange follow-up visits at the study site at Study Days 180; in the event, however, that a subject is remote from the site and unable to return within this window, a telephone call should be made to his/her local treating physician for as much information as possible to complete these visits.
- ^c Complete medical and surgical history, including history of GvHD diagnosis (with stages by organ), hepatic, renal or cardiovascular disease, history of chronic diseases, history of diabetes, alcoholism or drug abuse, and non-disease relevant clinical history.
- ^d Date of transplant, donor relation, gender and date of birth, human leukocyte antigen matching, stem cell source, diagnosis, phase of the disease at the time of transplant, assessment of engraftment, date of neutrophil and platelet engraftment, date of donor chimerism assessment and details of donor lymphocyte infusion.
- ^e Record administration of medication (date, dose, variations) associated with transplant/post-transplant: conditioning regimen, GvHD prophylaxis and all drugs administered to the subject.
- ^f Record other prior and concomitant medications, including history of adverse reactions to medications at each visit through Day 58 or up to 30 days after the last dose of study treatment, whichever is later.
- ^g The assessments should be conducted on the same day as the BEGEDINA infusion or conventional treatment, when applicable.
- ^h A complete physical examination will include, at a minimum, assessment of the following systems: skin, head, ears, eyes, nose, and throat, respiratory system, cardiovascular system, gastrointestinal system, neurological condition, blood and lymphatic systems, and the musculoskeletal system.
- ⁱ Height only measured at Screening.
- ^j Vital signs (systolic and diastolic blood pressure, heart rate, respiratory rate, body temperature) and oxygen saturation to be performed prior to BEGEDINA or conventional treatment administration, 30 and 60 minutes from the start of the first administration and prior to and at 60 minutes from the start of subsequent administrations. Patients in the BEGEDINA arm will continue to be monitored (under hospital observation) through 2 hours after the start of infusion.
- ^k ECG is to be performed at on Study Day 1 (prior to start of BEGEDINA or conventional therapy), and on Study Days 5, 14, and 28. A window of 7 days for screening ECG results collected per standard of care prior to Screening visit is allowed. For patients in the BEGEDINA arm, the ECG on Study Days 5, 14, and 28 is to be performed after completion of the infusion (and at the time of the post-infusion PK draw, when applicable). See section 6.2.3.2 for details.
- ^l To be coordinated with local routine/standard collections, as is possible, with window ± 2 days.
- Hematology: Basophils, eosinophils, hematocrit, hemoglobin, lymphocytes, monocytes, neutrophils, platelets, red blood cells, total white blood cells, mean corpuscular volume, mean corpuscular hemoglobin concentration, mean corpuscular hemoglobin. Optional (if routinely available): mean platelet volume, red blood cell distribution width, prothrombin time, prothrombin time-international normalization ratio. Serum chemistry: Albumin, alkaline phosphatase, alanine aminotransferase, aspartate aminotransferase, bicarbonate, blood urea nitrogen, calcium, chloride, creatinine, direct bilirubin, glucose, inorganic phosphorus, lactate dehydrogenase, lipase, potassium, sodium, total bilirubin, total protein, gamma-glutamyl, creatine phosphokinase. Lipid panel: Total cholesterol, high density lipoprotein, low density lipoprotein, triglycerides. Urinalysis: Blood, glucose, ketones, microscopic exam, pH, protein, specific gravity, bilirubin. To be coordinated with local routine/standard collections, as is possible, with window ± 2 days.
- ^m Serum pregnancy test (beta-human chorionic gonadotropin) at screening only for women of childbearing potential only who have not been started on an anti-ovulatory regimen prior to initiation of chemo-inductive regimen.
- ⁿ Glucose metabolism will be assessed through the evaluation of fasting glucose, insulin, c-peptide, glycosylated hemoglobin and Homeostasis Model Assessment (HOMA) calculation and through glucose in urine. Blood and urine samples for these assessments will be collected at baseline and on Study Days 28 and 180 (see Section 6.2.2.4 for details).
- ^o Infection markers (most recently available results, as collected per standard of care, with window up to 90 days pre-study screening): HIV-1 Ab, HIV-2 Ab, HBsAg, HBe Ab, cytomegalovirus (CMV) DNA, HCV Ab, EBV DNA, erythrocyte sedimentation rate, C-reactive protein. CMV and EBV to be taken for analysis on Study Day 28 and Day 56 (window ± 2).
- ^p A copy of the Karnofsky Performance Status scale is provided in Appendix 2 (see Section 12.2)
- ^q GvHD assessment and staging using the modified International Bone Marrow Transplant Registry (IBMTR) index and according to common criteria of Glucksberg to be performed by a physician (see Section 6.1.1.1.1).

^r Quality of Life (QoL) will be assessed using the Short Form 36 test. A copy of this questionnaire is provided in Appendix 3 (see Section 12.3).

^s For subjects in the BEGEDINA arm only: Blood sample for PK measurements will be collected prior to and 15 minutes post-infusion, on Study Days 1, 5, 10, 14, 17, 21, 24, and 28 (see Section 6.3 for details). A window (+/- 1 day) is permitted from Day to Day 28, however, all efforts should be made to plan these doses with at least 48 hours between doses.

^t For subjects in the BEGEDINA arm only: Blood sample for HAMA measurements will be taken before the first infusion and after the fifth infusion and on Study Days 10, 14, 17, 21, 24, 28, 56, and 90 (see Section **Errore. L'origine riferimento non è stata trovata.** for details). On study days in which BEGEDINA infusion is planned, the sample will be drawn to infusion (i.e., earlier that day or immediately prior to the infusion).

^u Note that during the administration of BEGEDINA/conventional treatment, the response to treatment is to be done at Study Day 28.

^v Subjects are to be assessed at all visits for the appearance of chronic GvHD.

^w Record all AEs observed in both arms during the study, from the time that informed consent is signed through Study Day 58 or up to 30 days after the last dose of study treatment, whichever is later. Any ongoing adverse drug reactions (ADRs) and/or SAEs will be followed until resolution (for a maximum to Study Day 180). Second malignancies and deaths will be recorded as SAEs through Study Day 180.

^x Laboratory safety parameters at Day 180: Glucose to be collected; other laboratory safety parameters are optional.

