included in safety (SAF) evaluations. One of the 13 treated subjects was determined to have been enrolled with chronic, not acute GvHD, and was alive and evaluable at 1 year but is excluded from the efficacy Full Analysis Set (FAS). Of the 12 subjects in the FAS, all were evaluable for GvHD through Day +30; 7 subjects were alive and evaluable through Day +180 and 4 subjects were alive and evaluable at Day +365.

Table 1 Subject Disposition (Pilot Study, EudraCT No. 2007-005809-21)

	Subject Disposition
Enrolled, n	14
Treated, n (%)	13 (92.9%)
Completed 1-year follow-up, n (%)	
No	9 (64.3%)
Yes	5 (35.7%)
Reason for discontinuation, n (%)	
Death	8 (57.1%)
New pathology	1 (7.1%)

Abbreviations: n, number of patients.

Source: Clinical study report, EudraCT No. 2007-005809-21, Table 4.

Efficacy Results

In the 12 FAS subjects, a response to BEGEDINA treatment was seen in 7 (58.3%) subjects at Day 10 and in 10 subjects (83.3%) at Day 30.

At Day +180, 7/12 (58.3%) subjects were alive and at Day +365, 4/12 (33.3 %) were alive.

Eight subjects (66.7%) died during the study; none of the deaths were considered related to BEGEDINA treatment by the investigator. The mean (STD) OS in the 8 subjects who died was 169.3 days (median 145.0 days; range 104-284 days (Table 2). The cause of death was transplant-related mortality (TRM) in 4 subjects (2 due to GvHD; 2 due to an infection) and relapse of the original disease in 4 subjects.

Table 2 Overall Survival Full Analysis Set (Pilot Study, EudraCT No. 2007-005809-21)

	Statistic	Full Analysis Set (N=12)
Death		
No	n (%)	4 (33.3%)
Yes	n (%)	8 (66.7%)
Overall survival (days)		
	n	8
	Mean (STD)	169.3 (69.1)
	Median	145.0
	Min, max	104, 284

Abbreviations: N, total number of patients; n, number of patients; STD, standard deviation.

Source: Clinical study report Addendum1, EudraCT No. 2007-005809-21, Table 14.2.4

Pharmacokinetic Results

Pharmacokinetic data were available from 11 subjects, of whom 3 received a second cycle of treatment.

A 2-compartment, open-model seemed to adequately describe the trend of serum concentrations of BEGEDINA during multiple dosing (2 mg once a day for 5 consecutive days) and during follow-up.

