Source: Clinical study report, EudraCT No. 2007-005809-21, Table 14.3.1.5.

Deaths

Death occurred in 5 subjects (38.5%) by Day 180, and in 8 subjects (61.5%) by Day +365 (Table 4). The causes of death (Day +365) were:

- Relapsed leukemia
- Leukemia
- Acute respiratory failure complicating pneumonia
- GvHD (primary cause) and gastric-enterorrhage (secondary cause)
- Disease progression and pneumonia with respiratory failure
- Acute GvHD
- Bronchopneumonia and acute respiratory failure
- Leukemia relapse (primary cause) and infection (secondary cause)

Serious adverse events

A total of 27 serious adverse events (SAEs) were reported in 9 subjects (69.2%). The most commonly reported SAEs by preferred term were bronchopneumonia (3 subjects, 23.1%) and dyspnea (2 subjects, 15.4%). None of the other SAEs by preferred term were reported in more than one subject each. None of the SAEs was considered as treatment-related.

Clinical laboratory findings

Individual Clinically Significant Abnormalities

Clinical laboratory parameter values that were considered as clinically significant and reported as AEs are summarized in Table 8. Only one case of anemia among the clinically significant abnormalities of laboratory parameters was considered as treatment-related.

Table 8 Incidence of Clinically Significant Laboratory Abnormalities Reported as Adverse Events (Safety Population)

System Organ Class Preferred Term	Safety Population (N=13) N (%)
Blood and Lymphatic System Disorders	
Anaemia	2 (15.4%) 2
Leukocytosis	1 (7.7%) 1
Leukopenia	4 (30.8%) 8
Pancytopenia	4 (30.8%) 5
Thrombocytopenia	3 (23.1%) 4
Investigations	
Alanine aminotransferase increased	1 (7.7%) 1
Blood alkaline phosphatase increased	1 (7.7%) 1
Blood bilirubin increased	4 (30.8%)
Blood creatinine increased	3 (23.1%) 6
Blood glucose increased	1 (7.7%) 1
Gamma-glutamyltransferase increased	5 (38.5%) 12
Haemoglobin decreased	2 (15.4%) 2
Hepatic enzyme increased	2 (15.4%) 2
Platelet count decreased	2 (15.4%) 2
Transaminases increased	3 (23.1%) 11
Metabolism and Nutrition Disorders	
Hyperglycaemia	1 (7.7%) 1
Hyperkalaemia	2 (15.4%) 2
Hypermagnesaemia	1 (7.7%) 1

Abbreviations: E, number of events; N, number of subjects.

Source: Clinical study report, EudraCT No. 2007-005809-21, Table 14.3.1.2.

Vital signs

There were no treatment-related abnormalities of vital signs parameters in any subject.

Human anti-mouse antibodies (HAMA)

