2.3 Risk Assessment

Steroid-resistant acute GvHD is associated with a high rate of morbidity and mortality, primarily from infections and/or multi-organ failure. Currently, there are no approved second-line regimens for treating subjects who develop steroid-resistant acute GvHD and those second-line therapies that are administered are largely unsatisfactory in terms of efficacy. For 30% of subjects, survival is no more than 1 year (Qian et al., 2013).

Any clinically relevant result in this population would be of significant benefit as it would offer a clinically relevant advantage for steroid-resistant acute GvHD patients.

The dose-finding study confirmed that BEGEDINA binds to circulating CD26+ T lymphocytes in patients with steroid-resistant acute GvHD. The efficacy endpoint was overall response (OR), which included patients with CR or PR to the BEGEDINA treatment (resolution of all signs of GvHD or improvement in grading of GvHD). Furthermore, the transplant mortality rate represents another efficacy endpoint to confirm the survival benefit.

The response rate on Study Day 28 for adults given BEGEDINA at the recommended schedule (3 mg/m² on Days +1, +2, +3, +4, and +5 and then on Days +10, +14, +17, +21, +24, and +28, considering Day +1 as the first day of treatment with BEGEDINA) was 85.7% and TRM at Day 180 was 28.6%.

Thus, if the efficacy of BEGEDINA can be confirmed in this study, it may provide benefit to this group of subjects in whom no satisfactory treatment options are available.

In clinical studies conducted to date, BEGEDINA has shown a good safety and tolerability profile; there was no evidence that there was an increased risk of toxicity at the higher doses.

This study will be performed in compliance with the protocol, ICH Good Clinical Practice (GCP) and applicable regulatory requirements, including the 2001/20/CE European Directive and the US FDA directive 21 CFR 314.126 - Adequate and well-controlled studies.

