6.2 Safety

6.2.1 Adverse Events

The investigator is responsible for recording all AEs observed in during the study, from the time that informed consent is signed through Study Day 58 or up to 30 days after the last dose of study treatment, whichever is later; at that time, any ongoing adverse drug reaction (ADR) and/or SAE event are to be followed until resolution (up to Study Day 180). AEs will be recorded in the subject's eCRF.

Second malignancies and deaths will be recorded as SAEs through Study Day 180.

Information about all AEs, whether volunteered by the subject, discovered by investigator questioning, or detected through physical examination, laboratory test or other means, will be collected and recorded on the AE page of the eCRF and followed as appropriate.

Diagnostic and therapeutic non-invasive and invasive (i.e. surgical) procedures will not be reported as AEs. However, the medical condition for which the procedure was performed must be reported if it meets the definition of an AE, unless it is a pre-existing (prior to stem cell transplantation (SCT)/chemotherapy) condition.

Underlying disease being studied (GvHD) will not be reported as an AE, unless is deemed as more severe than expected.

Medical conditions/diseases present before starting study drug are only considered AEs if they worsen after starting study treatment.

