6.2.1.2 Reporting of Adverse Events

All AEs occurred during the study, from the time that informed consent is signed through Study Day 58 or up to 30 days after the last dose of study treatment (whichever is later), and regardless of severity, are to be recorded on the appropriate AE pages (either ‘serious’ or ‘non-serious’) in the eCRF.

The investigator should complete all the details requested including dates of onset, severity, action taken, outcome, relationship to study drug. Each event should be recorded separately.

Further instructions are available in the training materials (i.e. eCRF and SAE Completion Guidelines).

6.2.1.3 Reporting of Serious Adverse Events and Unexpected Adverse Drug Reactions to the Regulatory Authorities and Investigators

All SAEs have to be reported, whether or not considered causally related to the IMP, or to the study procedure(s). All SAEs will be recorded in the eCRF.

If any SAE occurs in the course of the study, then investigators or other site personnel inform appropriate ADIENNE representatives immediately, or **no later than 24 hours** of when he or she becomes aware of it.

The designated ADIENNE representative works with the investigator to ensure that all the necessary information is provided to the ADIENNE Patient Safety data entry site **within one calendar day** of initial receipt for fatal and life-threatening events **and within 5 calendar days** of initial receipt for all other SAEs.

For fatal or life-threatening AEs where important or relevant information is missing, active follow-up is undertaken immediately. Investigators or other site personnel inform ADIENNE representatives of any follow-up information on a previously reported SAE immediately, or **no later than 24 hours** of when he or she becomes aware of it.

The reference document for definition of expectedness/listedness is the IB for bebelomab.

Investigators should follow local IRB/EC guidelines regarding reporting of AEs to their IRB/EC.

The Sponsor will be responsible for safety reporting to Competent Authorities, Investigators and IRBs/ECs as per requirements specified in the European Directive 2001/20/EC and in the Code of Federal Regulations 312.32 and associated guidances. In particular the Sponsor will be responsible for reporting:

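### New non-fatal SAEs need not be recorded after a cut-off tied to last dose (as early as Day 58), which conflicts with the plan for safety data to Day 180 and can make SAE capture differ between arms

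*Combined protocol and SAP*

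**What the plan says.** Two sets of passages describe how long safety events are collected.

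- **To Day 180, or with no end date.** Section 4.1 describes long-term follow-up for "glucose metabolism, health outcomes and safety data out to Study Day 180". Section 6.2.1.3 requires all SAEs to be reported and entered in the eCRF, with the trigger "If any SAE occurs in the course of the study". Section 4.4.4 defines each subject's study as running from consent to the last follow-up visit, which is Day 180.
- **A shorter window.** Section 6.2.1 records AEs from consent "through Study Day 58 or up to 30 days after the last dose of study treatment, whichever is later". Section 6.2.1.2, the AE row of Table 19 and its footnote w repeat this, with no general exception for SAEs. Reactions and SAEs still open at that point are followed to resolution, at most to Day 180. The only new events kept beyond the window are these: "Second malignancies and deaths will be recorded as SAEs through Study Day 180".

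Section 3.1.3 makes comparison of safety and tolerability between the arms a secondary objective. Section 2.3 states the disease risk as follows: "Steroid-resistant acute GvHD is associated with a high rate of morbidity and mortality, primarily from infections and/or multi-organ failure".

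**The concern.** Under sections 6.2.1 and 6.2.1.2, a BEGEDINA subject without retreatment who develops septic shock or a new organ failure on Day 75 and survives has nothing that must be recorded. Under section 6.2.1.3, the same event is reportable. About 30 sites could resolve this differently, leaving late SAE data that are neither complete nor cleanly absent.

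The window is also tied to each subject's last dose. Treatment duration is fixed for an initial BEGEDINA course, longer after flare retreatment, and open-ended for conventional therapy. The period in which an SAE can be counted may therefore differ by arm for reasons unrelated to risk. Section 8.3.7 tabulates incidence over all exposed subjects and describes no adjustment for differing observation time.

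**Working it through.** **1. When recording closes.** Let L be the Study Day of the last dose. By section 6.2.1, the closing day is the later of 58 and L + 30. The last initial BEGEDINA dose is on Day 28 (section 5.1.1). A flare after Day 28 and before Day 90 permits a second full course, whose last dose falls 27 days after its first (section 5.9). Conventional therapy may be continued or restarted at the investigator's judgment (section 5.9).

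| Case | L | Closing day | Share of 180 days | Days left |
|---|---|---|---|---|
| BEGEDINA, initial course only | 28 | 28 + 30 = 58 | 58/180 = 32% | 122 |
| BEGEDINA, full flare course from Day 29 | 29 + 27 = 56 | 56 + 30 = 86 | 86/180 = 48% | 94 |
| BEGEDINA, full flare course from Day 89 | 89 + 27 = 116 | 116 + 30 = 146 | 146/180 = 81% | 34 |
| Conventional, last dose by Day 28 | up to 28 | 58 | 32% | 122 |
| Conventional, still dosed at Day 150 (illustration) | 150 | 150 + 30 = 180 | 100% | 0 |

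Day 58 is thus the earliest close, not the general one.

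**2. What unequal windows can do.** As an illustration, assume a constant rate of new SAEs that is the same for everyone. Expected recorded events are then proportional to window length. Relative to a Day 58 close, the ratio is 86/58 = 1.5, 146/58 = 2.5 or 180/58 = 3.1. These are event-count ratios between individual subjects, not a predicted difference between arms. The arm difference depends on retreatment and on conventional treatment durations, which the documents do not give, so its direction is unknown.

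**3. Does risk continue after Day 58?** Table 11 gives dose-finding death times by cohort.

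- DL1: 28, 45 and 89. Mean (28 + 45 + 89)/3 = 54.0 and SD 31.5, as printed.
- DL2: 24.
- DL2bis: 17 and 116. Mean (17 + 116)/2 = 66.5 and SD 70.0, as printed.

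That is 6 deaths, as stated, with 2 of 6 after Day 58 (Days 89 and 116). In the pilot, "Death occurred in 5 subjects (38.5%) by Day 180", and time to death had "median 145.0 days; range 104-284 days", so all 5 came after Day 58. Together, (5 + 2)/(5 + 6) = 7/11 = 64%, exact 95% interval 31% to 89%. The count is the same for any cut-off from Day 45 to Day 88. It assumes that survival days run from the first BEGEDINA dose.

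**4. What those deaths were.** One DL2bis death was from sepsis with multiple organ dysfunction and the other from acute GvHD. The GvHD death was on Day 17, so the sepsis death was on Day 116. In the pilot, 4 of 8 deaths were relapse, 2 GvHD and 2 infection, with no dates by cause. Of the 5 pilot deaths by Day 180, 0 to 2 were therefore transplant-related infection deaths. On that classification, 1 to 3 of the 11 were infection or organ-failure deaths after Day 58. Separately, four of the eight pilot cause-of-death entries mention pneumonia, bronchopneumonia or infection. Only 8 - 5 = 3 deaths came after Day 180, so at least one of those four fell between Day 104 and Day 180.

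**The case against.** The strongest reply is that late safety is substantially covered and that window length is partly preference. Deaths and second malignancies are recorded as SAEs to Day 180, and open SAEs are followed. Section 6.2.3.3 sends significant new examination findings that meet the AE or SAE definition to the AE form with no end date, and examinations are scheduled at Days 90 and 180. Section 6.2.2 reviews laboratory results at all timepoints. Thirty days is about 17 of the stated 1.8-day half-lives (30/1.8 = 16.7). All of this stands. It makes the text inconsistent rather than a clean stop, and it supports a short window for non-serious AEs. It does not settle which rule a site follows for a new survived SAE on Day 75, nor does it make the windows equal between arms.

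A reader might infer several stronger points that the documents do not support:

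- **That 7 of 11 measures what is missed.** All seven events are deaths, and this protocol would capture them as SAEs. They are few and uncontrolled, and relapse was a common cause in the pilot. The pilot used a different regimen, and 4 of 6 dose-finding deaths came by Day 45.
- **That a late excess of TRM could not be explained.** Fatal events carry their cause (section 6.2.1.1), and AEs leading to death are tabulated by arm (section 8.3.7). Only new non-fatal events that preceded death may be absent.
- **That the DSMB would see late harm only as deaths.** Its data are set in a separate charter (section 6.2.6) that is not among the documents.
- **That the whole trial observes SAEs for only a third of follow-up.** The 32% applies to the earliest close.

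**Conclusion.** The concern holds in a limited form. Sections 6.2.1 and 6.2.1.2 and Table 19 footnote w do not require recording of new non-fatal SAEs, other than second malignancies, after Day 58 or 30 days after last dose, whichever is later. Sections 4.1 and 6.2.1.3 point the other way. The unrecorded stretch can be up to 122 of 180 days. It shrinks to between 94 and 34 days after a full flare course, and it has no fixed length in the conventional arm. The bias in the safety comparison is possible rather than shown, and neither its size nor its direction can be derived from the documents. The earlier deaths, including the Day 116 sepsis death, establish only that risk persists beyond Day 58. The retreatment closing days assume that a full course starts on the day of flare. This is a cheap improvement: it does not affect the primary endpoints.

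**What to change.** Reconcile sections 4.1, 6.2.1, 6.2.1.2, 6.2.1.3 and 6.2.1.4 and Table 19 (AE row and footnote w) on one fixed SAE recording period, from consent through Study Day 180, identical in both arms and independent of last dose. Collect new SAEs at the existing Day 56, 90 and 180 visits, and ask about them when Day 180 is replaced by the telephone contact allowed in footnote b. Keep the shorter window for non-serious AEs. In section 8.3.7, tabulate SAEs and serious infections by arm to Day 58 and to Day 180, so that both comparisons rest on equal windows. Concomitant-medication recording closes with the present window (section 5.7), so the amendment should say whether treatments for late SAEs are captured on the SAE form.

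The cost is amendment wording, additional SAE forms after the present cut-off and more pharmacovigilance processing. No new visits or procedures are needed.
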